Baseline and Follow-up Assessment: After meeting full criteria and consenting to participate in the study participants will be asked to complete 4 psychosocial interviews, T1 (baseline), T2-T4 (follow-ups). The interviews may vary in length and may take up to 2.5 hours to complete, depending on the ability of the participants to answer each question. The following information will be collected:

Primary Outcomes: PC Symptom Burden and HRQoL.

Symptom burden is assessed using the EPIC-Short Form Sexual Summary (EPIC-S) score and the EPIC-Short Form urinary domain score (EPIC-UIN). 168,170,147 HRQoL will be measured with the Functional Assessment of Cancer Therapy-Prostate (FACT-P including 4 domains of the FACT-G)⁴⁰ and PROMIS short forms for pain and fatigue. 148 The FACT-P and PROMIS measures have been used to assess functioning (e.g., nausea, pain, fatigue, life engagement, work and/or daily activities) in cancer survivors and are available in Spanish. 148,149

Possible Moderators of C-CBSM's Effects on our Primary Outcomes.

Socioeconomic Status (SES): We will collect SES by gathering information on household income.

Treatment Type: We will assess treatment type as surgery (e.g., radical retropubic, radical perineal, laparoscopic, robotic assisted), radiation (e.g., external beam radiation therapy; 3- dimensional conformal radiation; intensity modulated; proton beam; brachytherapy), and/ or hormone therapy (e.g., LHRH analogs & antagonists; antiandrogens). We will assess whether SES, and/or type of treatment modify the effects of C-CBSM. We will also explore whether major Hispanic origin categories (e.g., Mexican, Cuban, Puerto Rican, Central & South American) and acculturation moderate the effects of CBSM.

COVID-19 Impact: We will use the COVID-19: Impact of the Pandemic and HRQOL in Cancer Patients and Survivors moderate the effects of the interventions.

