Because the inclusion criteria for this study requires that the participants be Spanish speakers, all participants will be screened in Spanish by Spanish speaking research staff. Upon meeting initial eligibility via EMRs (see protocol section Recruitment), research staff will conduct phone screening to assess symptom burden using the EPIC-S^{168,169} and -UIN^{170,169} for sexual and urinary function and Short Portable Mental Status Questionnaire (SPMSQ) to assess cognitive function and detect impairment. We anticipate that ~70% of participants score in this range based on our prior work in PC. The Short Portable Mental Status Questionnaire (SPMSQ) will measure orientation, memory, attention, naming, comprehension capabilities and is sensitive to Hispanic populations; accounting for higher illiteracy rates in this community. The Short Portable Mental Status Questionnaire (SPMSQ) will be used as a screening instrument for dementia. The SPMSQ is a 10- item test that assesses orientation, concentration, immediate and delayed verbal memory, language, 3- step praxis and constructional apraxia. Literate individuals scoring >3 on the SPMSQ will be excluded, or as per PI discretion based on a case by case review. SPMSQ is also calibrated to take into illiteracy into account, for illiterate individuals scoring >4 they will be excluded or as per PI discretion based on a case by case review. The screening process will take approximately 15-20 minutes (please refer to the screening form).

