The informed consent process will occur after eligibility has been fully established by the PI and/or Co-PI. The potential participant may be consented at the beginning of the first in-person assessment meeting or if he is not able to come in person to a scheduled assessment consent will be obtained remotely via E-Consent (RedCap link sent to the individual's email) or through Zoom. If the individual does not have a computer to provide consent via E-consent or Zoom, he will be mailed 2 copies of the consent form. All remote consents through Zoom or US mail will involve a 3-party telephone call with the potential participant, the person obtaining the consent, and a witness to review the consent documents and answer any questions the potential participant may have. We will use an IC Review

Checklist to ensure that all sections of the consent form are thoroughly reviewed and that individuals will be given ample time to ask any questions about the study. The IC Review Checklist will also have a statement describing the consent process, including the return method after signing the consent form or if the participant has difficulties in sending us their signed consent form. Participants in this study will be consented using IRB approved informed consent form (ICF) documents in Spanish or if they prefer in English as long as the participant agrees to participate in groups in Spanish. Research staff will review the ICF with the participant and assure that participants have a full understanding of the informed consent by asking them several questions to ascertain comprehension before having them sign. Participants will also be asked to consent to videotaping of sessions for clinical supervision purposes and informed that all videos are held in the highest regard of confidentiality and destroyed upon completion of the study. If participant decline to sign the consent to video, they will not be excluded from the study and no videos will be done where the individual declining to be videotaped is present. A copy of the consent form will be provided to the participant for their record.

Assessment and Data collection:

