Participants will be randomized by cluster randomization (C-CBSM or CBSM) to balance treatment type across conditions. We project to retain 140 participants at our 12-months post-intervention assessment visit (T4). All participants will be asked to participate in 10-weekly 90-minute in person sessions targeting CBT based skills for managing stress and self-management in one of two experimental conditions—a linguistically translated (Spanish) and culturally adapted cognitive behavioral stress and self-management (CBSM) condition (i.e., C-CBSM) or in a standard version of CBSM that is only linguistically translated (CBSM). Following the baseline visit (T1, pre C-CBSM or CBSM), participants are randomly assigned into one of our experimental or control condition groups.

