To Test Exploratory Hypotheses. Aim 3: For Hypotheses 3, the linear mixed model will include fixed effects for the experimental group (C-CBSM vs. CBSM) and observation time (T1-T4), and random effect for person with a compound symmetry covariance structure for the repeated residuals within person. A group by time interaction and post-hoc tests on this model effect will indicate whether and how the time course of the dependent variable differs between the groups. Hypotheses 1-3 will all be analyzed in a similar manner using the outcome measures described in sections C.6.c (Primary Outcomes), C.6.d (Intervention Targets) and C.6.e (Inflammation) respectively. These measures include markers of symptom burden, systemic inflammation, and cytokine production following cellular activation with TLR ligands. Data from gene expression profiling are analyzed using advanced bioinformatics techniques, and described in C.6.e, and as reported previously by Antoni et al.¹²⁴ As each outcome across the different study hypotheses have been carefully selected to address a priori hypotheses, no adjustment for testing of multiple outcomes will be made. However, within the analysis of a specific outcome, Tukey or Bonferroni adjustment will be made for the multiple tests across different time points. The power calculation below adjusts for this multiplicity. Aims 4a-4c: These hypotheses involve tests of proposed mediators of C-CBSM's effect on our primary outcomes. To test mediation with LGM, individual change trajectory (in each outcome of interest) is characterized by an intercept and a slope factor. The overall pattern of change (e.g., linear, quadratic, etc., as informed by analyses for Aims 1-3) for the whole group can be specified by a particular set of coefficients associated with the slope factor. First, we will specify a growth curve model for all participants with an intercept factor representing our outcome of interest at baseline, and the slope factor reflecting the change trajectory in our outcome measure from T1 to T4. For example, to test that increased stress management skills (e.g., MOCS) in the C-CBSM group accounts for reductions in symptom burden (e.g., EPIC-S), we will first test a LGM model without the stress management skills (the mediator) and then test the model with change in stress management skills from T1 to T4. In the model without the stress management skills, we expect that group assignment is not related to baseline symptom burden, but that group assignment will be related to a greater negative change (reduction) in symptom burden scores. In the next step, we will add stress management skills and expect that after adding this mediator in the model, the path between group assignment and symptom burden slope will become non-significant, while the path between the mediator and symptom burden slope is significant thus suggesting mediation. This approach will be applied to test all mediation models in hypotheses 4a-4c. 191,192 Aim 5a-5b: To evaluate moderators and mechanistic pathways of C-CBSM's effects, we will use LMM and latent variable mediation models. For Hypothesis 5a, we will test moderation by including interaction terms between group assignment (C-CBSM vs. CBSM) and each moderator of interest (e.g., SES, acculturation, Hispanic ancestry, treatment type) within the LMM framework. These models will include fixed effects for group, time (T1-T4), the moderator, and the group × moderator and group × time × moderator interactions. A significant three-way interaction (group × time × moderator) will indicate that change in the outcome (e.g., inflammation, symptom burden, HRQoL) over time differs by both treatment group and the level of the moderator. Post-hoc comparisons will clarify the nature of the moderation effects across timepoints. For Hypothesis 5b, we will test whether improvements in cardiometabolic markers (e.g., lipids, fasting glucose, blood pressure) in the C-CBSM group are mediated by reductions in inflammation using SEM. Parallel process LGMs will estimate trajectories for inflammatory markers and cardiometabolic outcomes across time. The indirect effect from group assignment to cardiometabolic outcome slope via inflammation slope will be tested. This approach allows for simultaneous modeling of changes over time, capturing both within- and between-subject effects. Model fit will be evaluated using standard criteria (CFI > .95, RMSEA ≤ .05, SRMR < .08), and significance of indirect effects will be tested using bias-corrected bootstrapped confidence intervals.

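### EPIC-S and EPIC-UIN are read twice before randomisation, but the model treats T1 as a free response and ignores the screening score, leaving some precision unused

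*Combined protocol and SAP*

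**What the plan says.** **Two readings.** Under Formal Screening Protocol, "research staff will conduct phone screening to assess symptom burden using the EPIC-S" and the EPIC-UIN. Under Primary Outcomes, "Symptom burden is assessed using the EPIC-Short Form Sexual Summary (EPIC-S) score and the EPIC-Short Form urinary domain score (EPIC-UIN"), and the interviews run from T1 to T4.

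**Both before randomisation.** Consent Process: "The informed consent process will occur after eligibility has been fully established by the PI and/or Co-PI". Randomization Protocol: "Following the baseline visit (T1, pre C-CBSM or CBSM), participants are randomly assigned". The order is therefore screen, consent, T1, randomisation.

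**The model.** The paragraph To Test Exploratory Hypotheses specifies "fixed effects for the experimental group (C-CBSM vs. CBSM) and observation time (T1-T4), and random effect for person". Residuals are given equal correlation between all visits (compound symmetry), and the test is of the group-by-time interaction. The paragraph extends this to the primary hypothesis: "Hypotheses 1-3 will all be analyzed in a similar manner". Hypothesis 1 is stated as change from T1, and Power Analyses defines the effect size as the arm difference in mean change over the SD of change.

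**What is absent.** No section gives the screening EPIC scores a role in the analysis. The covariate paragraph is open-ended, gives SES and disease factors as examples, and admits variables correlated with the outcome at p<.10.

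**The concern.** T1 is one of the four response times and the group-by-time effects are unconstrained. With complete data, the T1-to-follow-up contrast therefore behaves like a change score, and all the noise in a single T1 reading passes into it. Randomisation makes the true pre-treatment means equal across arms, and the model does not use that fact. It also leaves aside a second pre-randomisation reading of the same instrument.

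The open covariate rule does not repair this. A screening score entered as a main effect shifts a man's T1 and follow-up values equally, so it drops out of the change contrast.

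Precision matters here because EPIC-S has no margin. Power Analyses derives a pilot effect of 0.40 for it. That equals the detectable effect at the 5% level and lies below the 0.49 quoted at 1%. The pilot's control was a one-day seminar, whereas this trial's comparator is an active programme.

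**Working it through.** **1. The plan's own figure.** With 100 per arm and 80% power, detectable effect = (z for alpha + 0.842) × √(2/100).
- 5% two-sided: (1.960 + 0.842) × 0.1414 = 0.396. The plan says 0.40.
- 1% two-sided: (2.576 + 0.842) × 0.1414 = 0.483, or 0.487 with the t distribution. The plan says 0.49.

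The figures reproduce, and they rest on change from one baseline.

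**2. Formulas.** Take one follow-up, unit variances, r = correlation of either baseline with follow-up, and rb = correlation between the two baselines. The documents give neither, so I assume r = 0.5-0.7 and rb = 0.7-0.9.
- Change from T1: 2(1 − r)
- Conditioning on T1: 1 − r²
- Conditioning on T1 and screen: 1 − 2r²/(1 + rb)
- T1 left as a free response, screening score added with visit interaction: 2(1 − r) − (r − rb)²

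**3. Central case, r = 0.6, rb = 0.8.**
- Change from T1: 0.80
- T1 alone: 0.64, a cut of 20%
- Both readings: 1 − 0.72/1.8 = 0.60, a cut of 25%
- Added by the screening score after T1: 1 − 0.60/0.64 = 6.25%, about 3% in standard error
- Free T1 plus screening score: 0.80 − 0.04 = 0.76, a cut of 5%

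**4. Range.** The third and fourth columns are cuts against change from T1. The fifth is the further cut relative to T1 alone, with its worth in men as 140 × (variance on T1 / variance on both − 1).

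| r | rb | T1 alone | Both readings | Added by screen | Men of 140 | Free T1 plus screen |
|---|---|---|---|---|---|---|
| 0.5 | 0.7 | 25% | 29% | 6% | 8.8 | 4% |
| 0.5 | 0.9 | 25% | 26% | 2% | 2.5 | 16% |
| 0.6 | 0.8 | 20% | 25% | 6% | 9.3 | 5% |
| 0.7 | 0.7 | 15% | 29% | 17% | 28.6 | 0% |
| 0.7 | 0.9 | 15% | 19% | 5% | 7.5 | 7% |

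The last column is zero whenever r = rb, which is what compound symmetry implies.

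**5. Effect on power.** Hold the effect at 0.40 SD of T1 change, at the 5% level. Power = Φ(0.40 × √(n/2) / √ratio − 1.96), where ratio is the variance relative to change from T1. The 140 projected at T4 are taken as 70 per arm. Values are for r = 0.6, rb = 0.8.

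| Analysis | Ratio | 100 per arm | 70 per arm |
|---|---|---|---|
| Change from T1 | 1.00 | 80.7% | 65.8% |
| Conditioning on T1 | 0.80 | 88.5% | 75.4% |
| Conditioning on both | 0.75 | 90.4% | 78.0% |

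**6. Sensitivity of the screening score's added part.** With all three correlations at 0.6, the addition is 14%. If only the worst 70% on the screening score were enrolled, it falls to 9%. If the screen correlates 0.1-0.2 less with the other readings than they do with each other (0.6-0.7), it is 5%-10%. None of these figures allows for clustering by therapy group.

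**The case against.** **Most of the gain needs no screening data.** This stands. In the central case, T1 alone accounts for 20 of the 25 percentage points. The screening score is a small second step.

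**The gain is narrow and uncertain.** This also stands. It reaches EPIC-S and EPIC-UIN, not FACT-P or PROMIS, and both correlations are assumed. T1 may be taken at the office, at home, by Zoom or by phone, so the mode gap from the phone screen varies between men. Delivery in groups of 4-8 dilutes any individual-level gain.

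**Screening scores may be incomplete, or selected.** Partly stands. The screening form is not in the documents. The opening summary speaks of men with elevated symptom burden, and Formal Screening Protocol refers to a range it does not state, yet the eligibility list has no EPIC cut-off. If one is applied, the gain shrinks. Regression to the mean would be common to both arms and would not bias the comparison.

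**Stronger readings the documents do not support.**
- A reader might infer that ignoring the screening score biases or invalidates the primary test. It does not: change from T1 is a valid randomised comparison.
- A reader might also infer that simply adding the score to the planned model recovers the gain. While T1 remains a free response it recovers 0%-16%, and nothing under equal correlations.

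**Conclusion.** The point holds as an efficiency improvement on two primary outcomes. Treating both pre-randomisation readings as baselines would cut the variance of the EPIC contrasts by 19%-29% against change from T1 (25% at r = 0.6, rb = 0.8). Conditioning on T1 accounts for 15%-25%. The screening score takes a further 2%-17% off the remainder (6% centrally), worth about 9 men of 140, range 3-29. These figures assume the stated correlations, complete data at a single follow-up, no selection on the screen and no clustering. The last two, and differences in interview mode, would reduce what the screening score adds.

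**What to change.** For EPIC-S and EPIC-UIN, specify one of two analyses before outcomes are compared by arm:
- model T2-T4 with T1 and the screening score as covariates, each interacted with visit; or
- enter the screen and T1 as pre-randomisation responses, each with a mean constrained equal across arms, under an unstructured covariance so that the phone reading may correlate less.

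Where the screening score is missing, impute the pooled mean in the first form or rely on the likelihood in the second, so that no man is lost. If the screening data prove unusable, conditioning on T1 alone still secures most of the central-case gain.

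The cost is a short change to the analysis text, a merge of the screening records, and a check that those scores were retained. The sponsor should also confirm that answers given on verbal permission, before written consent (Pre-Screening Protocol), may be kept and analysed. No new visits or measurements are needed.

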Experimental Design. Our primary aim is to examine the effectiveness and incremental efficacy of a 10-week group-based, linguistically and culturally adapted cognitive behavioral stress and self- management intervention (C-CBSM) vs. a linguistically translated standard CBSM (no cultural adaptation) on symptom burden and HRQOL in Hispanic men treated for localized PC. This is randomized control trial (RCT) with a 2x4 design with group assignment (C-CBSM vs. CBSM) as the between-group factor and time (baseline [T1], post-intervention [T2], 6-mos. [T3] & 12-mos [T4]. Post intervention [T4]) as the within-group factor. Primary outcomes are symptom burden (i.e., urinary & sexual function) and HRQoL (e.g., physical, social, emotional & functional). We will make every effort to engage and promote participation in all 10 sessions however we anticipate that some cases will not be able to attend all sessions due to multiple circumstances, such as change in employment or work schedule, health issues, relocation, unforeseen transportation difficulties, family crisis, social/environmental/health crisis (COVID-19), etc. This study uses an intent to treat intervention design model thus participation in all sessions may differ for some individuals. We estimate attrition at ~22% over the study although our prior rate is closer to 10%. Cluster randomization will occur by group type (C-CBSM vs. CBSM).

Experimental Conditions:

CBSM. The standard English language^{59,60} intervention was developed for stress management, risk reduction, health maintenance and self-management by providing relaxation training and CBT-based strategies to improve symptom management, interpersonal adjustment and HRQoL, and reduce arousal and negative mood in men treated for PC. This standard, not culturally-adapted CBSM underwent forward and backward translation by Action Translation Services¹⁷² with internal verification.

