conference platform will use a private phone line where participants are called to join the group meeting. Groups that are conducted via a video conferencing format will be provided with a study tablet that connects to a secure conference network (Vidyo). The tablets connect to an AES encrypted channel which allows participants to access a secured video conferencing room (secured with pin) with the ability for the therapist to lock the room further after all the participants have entered before start of any group session. Each tablet will have a personalized pin number for participants to access its features. The pin numbers are reset upon completion of the intervention period and return of the tablet to our technical team. The delivery modality (face-to face, phone or through video conferencing) will be at the discretion of the PI and Co-PIs.

CBSM and CCBSM intervention groups are composed of 4-8 participants lasting 90 minutes/session. In the first 30 minutes, participants are taught/discuss a new anxiety/arousal reduction technique whereas the latter 60 minutes focus on stress- and self-management. Disease course, symptom burden, communication with intimate partner and/or family members and health care provider, impact of stress on physical and mental health and symptoms, and management of symptom burden and decrements in HRQoL are used for educational purposes and as catalysts for CBSM techniques. Participants describe stressors with an emphasis on symptoms and disruption, HRQoL and their coping responses for in- session role-plays. Participants receive a participant workbook with all the relaxation and stress management didactics, homework, self-monitoring tools and exercises to implement skills learned in the CBSM sessions in their own "real world" settings. Homework assignments are considered a practice activity to be reviewed in group discussions, these are voluntary and not mandatory.

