
Preliminary Analyses and other Statistical Considerations. Descriptive statistics will be computed to ensure values are within expected ranges and to eliminate any errors. We will use PRELIS2^{193,194} to examine multivariate normality. Non-normally distributed variables will be transformed using log transformations. We will compute estimates of internal consistency (Chronbach's α) for all scales and composite scores. If reliability is <.70, we will evaluate the internal consistency of the measure and delete items or subscales as needed.¹⁹⁵

Power Analyses. The primary aim compares pre-post change in symptom burden scores between the randomized arms. A sample of 100 per arm is assumed, although T1-T3 time points will have larger samples. Power is based on the effect size defined as the group difference in the mean change divided by the standard deviation of the change. Power calculations are based on effects of the C-CBSM pilot study. With 100 per arm, there is 80% power to detect an effect size of 0.40 assuming a two-tailed test and a Type I error rate of 5%. Since multiple tests look at change in various post-intervention time points, using a Type I error rate of 1% results in a detectable effect size of 0.49. If effect sizes are calculated from Figure 6 from our preliminary work, then the observed effect sizes as defined above are 0.52 for FACT-G and 0.40 for EPIC-S. Effect sizes for subscales FACT-PWB and FACT-EWB are

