0.81 and 0.42 respectively. With greater effect sizes anticipated in the proposed study, the sample size of at least 100 per arm has sufficient power to detect differences even after adjusting for the analysis of change from baseline to post-intervention time points. Power for C-CBSM's effect on down regulation of inflammatory genes are based on Antoni et al.¹²⁴ study which indicated that the observed effect size was one standard deviation in a sample size of 45 in the experimental condition. Glucocorticoid receptor sensitivity demonstrated similar effects. With a T4 sample size of 100 in the C-CBSM group, effect sizes of 0.48 standard deviations are detectable with 80% power at a 2-tailed Type I error rate of 1%, so that expected effects will be detectable with sufficient power. While pilot data are not available for all outcome measures, the constant in the power calculation regardless of the outcome is the effect size expressed in terms of standard deviations, which is 0.40 or 0.49 depending on whether the Type I error rate is 5% or 1%.

Covariates, Cohort Effects, Intent to Treat & Missing Data. A number of variables (e.g., SES, disease factors) will be considered as possible covariates. These putative confounds will be entered as covariates if correlated with our outcomes (at p<.10). Random assignment should render groups equivalent on covariates and this will be verified post-hoc. We will test differences among cohorts who have completed our conditions by doing an ANOVA within each condition with k levels of cohort. If we find a cohort with differential outcomes (significant Condition x Cohort x Time interaction), we will conduct a Group x Time interaction tested within each cohort, and a Cohort x Time interaction tested within assignment. We have never observed a significant cohort effect in prior CBSM work. We will also use an intent-to-treat approach in that all participants will be retained in the analysis, including those with missing data at time points by using full information maximum likelihood (FIML) estimation. FIML, a recommended state-of-the-art method, 197,198 uses all available data for each participant and provides unbiased estimates of parameters when the data are missing at random.

Cost to the Participants:

There will be no cost to the participants for taking part in this study. All expenses related to the study activities, including laboratory tests done and lab materials.

Risk and Benefits:

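### Both arms are delivered in groups of 4-8 men and assigned by cluster, but the primary model and the power calculation treat the men as independent

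*Combined protocol and SAP*

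**What the plan says.** - **Assignment.** The Randomization Protocol section says: "Participants will be randomized by cluster randomization (C-CBSM or CBSM) to balance treatment type across conditions". The Experimental Design paragraph repeats that assignment is by cluster. The Randomization Protocol section also says that, after baseline, "participants are randomly assigned into one of our experimental or control condition groups", which can be read as assignment of individual men.
- **Delivery.** Under CBSM and CCBSM Format and Goals: "CBSM and CCBSM intervention groups are composed of 4-8 participants lasting 90 minutes/session".
- **Primary model.** The paragraph To Test Exploratory Hypotheses gives fixed effects for condition and time and a "random effect for person with a compound symmetry covariance structure for the repeated residuals within person". It says that Hypotheses 1-3 are all handled in this way, so it governs the primary aim.
- **Power.** Power Analyses states: "A sample of 100 per arm is assumed, although T1-T3 time points will have larger samples", and then: "With 100 per arm, there is 80% power to detect an effect size of 0.40 assuming a two-tailed test". At a 1% error rate the detectable effect is given as 0.49. No ICC, design effect or number of groups appears.
- **Cohort check.** The paragraph on covariates, cohort effects and missing data plans an ANOVA on cohort within each condition. It continues: "If we find a cohort with differential outcomes (significant Condition x Cohort x Time interaction), we will conduct a Group x Time interaction". It adds that earlier CBSM work never showed a significant cohort effect. Cohort is not defined.

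**The concern.** Men in one group share a facilitator, ten weeks of discussion and role-play, and possibly a delivery mode (in person, phone or video). Their follow-up scores can therefore be more alike than those of men in different groups. The person random effect and compound symmetry describe repeated measures on one man and do not allow for correlation between men.

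This omission matters under either reading of the assignment. If whole groups are randomised, the analysis ignores the unit of randomisation. If men are randomised individually, group delivery in both arms still induces correlation after assignment. A positive ICC makes the primary p-values too small and leaves the trial with less power than stated.

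**Working it through.** **Inputs from the plan:** 100 men per arm; effect size 0.40 in units of the SD of change, two-sided 5%, 80% power; 0.49 at 1%; groups of 4-8; 140 of 200 men projected at T4, which is 70% retention.

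**Assumed:** ICC of the change score, 0.01 to 0.10. The documents give none.

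**Step 1: reproduce the stated power.** A two-sample t-test with 100 independent men per arm (noncentral t) gives 80.4% power at 0.40 and 5%, and 80.5% at 0.49 and 1%. The plan's figures are therefore those for a design effect of 1.

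**Step 2: apply the design effect.** With m men per group:

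- DE = 1 + (m − 1) × ICC
- effective n per arm = 100 / DE
- true size of a nominal 5% test = 2 × [1 − Φ(1.960 / √DE)]; for a nominal 1% test, replace 1.960 by 2.576
- power from the noncentral t at the effective n

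For m = 6 and ICC 0.05: DE = 1 + 5 × 0.05 = 1.25; effective n = 100 / 1.25 = 80; 1.960 / √1.25 = 1.753, so the true size is 8.0%.

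| ICC (m = 6) | DE | Effective n per arm | True size, nominal 5% | True size, nominal 1% | Power at 0.40, 5% |
|---|---|---|---|---|---|
| 0.01 | 1.05 | 95 | 5.6% | 1.2% | 78% |
| 0.02 | 1.10 | 91 | 6.2% | 1.4% | 77% |
| 0.05 | 1.25 | 80 | 8.0% | 2.1% | 71% |
| 0.10 | 1.50 | 67 | 11.0% | 3.5% | 63% |

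Across m = 4 to 8, the true size at ICC 0.05 runs from 6.8% to 9.2% and power from 75% to 68%. At ICC 0.10 the ranges are 8.6% to 13.3% and 69% to 58%.

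**Step 3: simulate with uneven groups and dropout.** With 200 men in groups of 4-8 and 70% retention, a t-test that ignores groups had a true size of about 6%, 7% and 10% at ICC 0.02, 0.05 and 0.10. Dropout shrinks the groups and so softens the inflation slightly. A t-test on group means stayed near 5%.

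**Step 4: degrees of freedom if whole groups are randomised.** With m = 6 there are about 100 / 6 ≈ 17 groups per arm, or 32 degrees of freedom. Power at 0.40 is then 74%, 69% and 61% at ICC 0.02, 0.05 and 0.10.

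**Step 5: can the cohort check detect clustering?** If cohort means intervention group, take the within-condition ANOVA with k = 17 groups of m = 6. Its power is P(F > F_crit / [1 + m × ICC / (1 − ICC)]) on k − 1 = 16 and k(m − 1) = 85 degrees of freedom. This gives about 7%, 10%, 19% and 41% at ICC 0.01, 0.02, 0.05 and 0.10. The Condition × Cohort × Time term cannot be estimated on this reading, because each group belongs to only one condition. If cohort means recruitment wave, the term can be estimated only where both conditions run in the same wave. With one group per condition in a wave, each cell would hold 4-8 men.

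**The case against.** The harm depends on an ICC that the documents do not give, and the investigators report no significant cohort effect in earlier work. At ICC 0.01 the cost is small: a true size of 5.6% and about two points of power. At zero there is none. That stands, and the size of the problem should be read as conditional. The earlier experience is weak reassurance, however, since a screen of this kind misses an ICC of 0.05 about four times in five.

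The calculations use a single change score, whereas the plan tests several time points with a Tukey or Bonferroni adjustment. With three correlated change scores (correlation 0.5-0.7 assumed), each tested at 1%, the per-outcome family error ignoring groups is about 4% at ICC 0.02 and 5-6% at 0.05. So the strict 1% level used in the power section would absorb much of the inflation. Ordinary Bonferroni would not: the corresponding figures are about 6% and 8%. The analysis section commits only to Tukey or Bonferroni, and none of this restores the lost power.

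The unit of randomisation is also unclear. This affects the degrees of freedom, but not the need for a group term. Finally, two-level latent growth models with about 33 groups in total (200 / 6) are demanding. That is a fair caution, but it concerns the exploratory mediation aims and not the primary model.

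**Conclusion.** The concern holds. As written, neither the primary model nor the sample size allows for correlation within intervention groups, and the stated power is reproduced only for independent men. For groups of 6 and an assumed ICC of 0.02 to 0.10, the true size of a nominal 5% test is about 6% to 11%, and power at 0.40 is about 77% to 63%, before any loss to follow-up. The omission is certain from the text; its size depends on the ICC. The cohort check does not repair it. A non-significant result is likely even when clustering matters and leaves independence in place. A significant result leads to tests within cohorts, not to a corrected standard error for the primary contrast. Because the fault bears on the validity of the primary p-value, it should be corrected before outcome data are examined by arm.

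**What to change.** 1. In the linear mixed models for Hypotheses 1-3, add a random effect for intervention group nested in condition, acting on the follow-up scores, with Satterthwaite or Kenward-Roger degrees of freedom. Analyse each man in the group to which he was assigned.
2. Remove the cohort significance test as the gate for handling clustering. If recruitment wave is also of interest, define it separately.
3. State whether men or whole groups are randomised, and reconcile the wording within the Randomization Protocol section and with Experimental Design.
4. Restate the detectable effect over a range of ICCs, with the assumed group size and number of groups. As a guide, multiplying the plan's figures by √DE at 6 per group turns 0.40 into 0.42, 0.45 and 0.49 at ICC 0.02, 0.05 and 0.10, and turns 0.49 at the 1% level into 0.51, 0.55 and 0.60. Attrition comes on top of this.
5. In the latent growth models, use cluster-robust or two-level estimation where the number of groups supports it, and state the limitation where it does not.

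For the primary analysis the cost is a change of SAP wording and one more variance component. No new assessments are needed. The plan records attendance at each session, so group membership should be recoverable, but it should be confirmed as a field in the analysis data set. Standard errors will usually be somewhat larger and the stated power less favourable. The two-level latent growth models are the only demanding part.
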